### **Withdrawal from trial**

Subjects who withdraw/are withdrawn from the trial prior to first dose of IMP (randomisation) will be considered screening failures.

Subjects who withdraw from the trial for any reason should attend an early termination visit as soon as possible after last administration of IMP. Assessments/procedures to be conducted at this visit are listed in the schedule of trial procedures (Section 4). If the subject agrees, the investigator will review any AEs which will be followed up according to Section 13.7.

Details on data to be recorded in the eCRF for subjects who withdraw from the trial can be found in Section 11.7.

### **10.4 Lost to follow-up**

A subject will be considered lost to follow-up if they repeatedly fail to return for scheduled visits and if the trial site is not able to get in contact with the subject.

The following actions must be taken if a subject fails to return to the trial site for a required visit:

- The trial site must attempt to contact the subject and reschedule the missed visit as soon as possible and counsel the subject on the importance of maintaining the assigned visit schedule and ascertain whether or not the subject wishes to continue in the trial.
- Before a subject is deemed lost to follow-up, the investigator or designee must make every effort to regain contact with the subject (where possible, 3 telephone calls and, if necessary, a certified letter to the subject's last known mailing address or local equivalent method[s]). These contact attempts should be documented in the subject's medical record.

THIS DOCUMENT CONTAINS CONFIDENTIAL INFORMATION AND MUST NOT BE COPIED OR MADE AVAILABLE TO ANY THIRD PARTY WITHOUT THE PRIOR WRITTEN CONSENT OF THE LEO PHARMA GROUP

- Should the subject continue to be unreachable, they will be considered to have withdrawn from the trial with a primary reason of lost to follow-up.

[figure not shown]
THIS DOCUMENT CONTAINS CONFIDENTIAL INFORMATION AND MUST NOT BE COPIED OR MADE AVAILABLE TO ANY THIRD PARTY WITHOUT THE PRIOR WRITTEN CONSENT OF THE LEO PHARMA GROUP

## 11 Trial assessments and procedures

### 11.1 Overview

Assessments and procedures to be conducted at each visit are listed in the schedule of trial procedures (Section 4) and will be conducted in the order presented in [Panel 6](#). PROs to be completed at the trial site and investigator assessments of efficacy should be conducted at the same visit.

#### Panel 6: Sequence of assessments

a At the screening visit (at the earliest Week -4), the subject's eligibility to participate in the trial must be confirmed before any PROs are completed. PROs will be completed either in the eDiary or on an electronic device at the trial site.

b Laboratory assessments include PK and PD samples. PD samples include serum biomarkers, skin swabs, and tape strips.

c For the first 3 IMP treatment visits (i.e., Visits 3, 4, and 5) subjects will be monitored after IMP administration for immediate drug reactions for a minimum of 1 hour with vital signs taken immediately after IMP administration as well as after 30 minutes ( $\pm$  5 minutes) and after 1 hour ( $\pm$  5 minutes), or until stable, whichever is later.

Subjects participating in the trial will be under careful supervision of a qualified principal investigator who must be a dermatologist or an allergist. Investigators must be physicians and have experience in treating AD as well as documented experience with and/or training in the assessments used in this trial. All dermatologic assessments must be performed by a

THIS DOCUMENT CONTAINS CONFIDENTIAL INFORMATION AND MUST NOT BE COPIED OR MADE AVAILABLE TO ANY THIRD PARTY WITHOUT THE PRIOR WRITTEN CONSENT OF THE LEO PHARMA GROUP

dermatologist or an adequately qualified medical doctor (defined as someone with at least 1 year post graduate experience).

AEs must be assessed by a physician (Section 13.2).

To reduce inter-rater variability, the same investigator should, whenever possible, perform all the efficacy assessments for a given subject throughout the entire trial period.

The investigators performing the assessments must not be involved in the administration of IMP (Section 9.3.1).

## 11.2 Assessments performed only at screening/baseline

### 11.2.1 Demographics

The following demographic data will be recorded at screening (Section 4):

- Full date of birth (day, month, and year) or partial date of birth (only month and year, or only year), as per local legislation.
- Age (as on the day informed consent is signed, if full date of birth cannot be collected due to local legislation).
- Sex: female, male.
- Race: American Indian or Alaska native, Asian, Black or African American, native Hawaiian or other Pacific islander, White, other (if other, a specification should be provided).
- Ethnic origin (self-reported by the subject, Hispanic or Latino, not Hispanic or Latino), if allowed by the local legislation.

At baseline, only age will be recorded (Section 4).

### 11.2.2 Body assessment (height)

Height will be recorded according to the schedule of trial procedure (Section 4).

The subject's height (without shoes) will be measured.

### 11.2.3 Medical history

Medical history will be recorded according to the schedule of trial procedures (Section 4).

Relevant past and concurrent medical history must be recorded including all past and current skin disease history:

THIS DOCUMENT CONTAINS CONFIDENTIAL INFORMATION AND MUST NOT BE COPIED OR MADE AVAILABLE TO ANY THIRD PARTY WITHOUT THE PRIOR WRITTEN CONSENT OF THE LEO PHARMA GROUP

- Atopy history:
  - Age at first onset of AD.
  - Previous AD treatments (e.g., dupilumab, cyclosporine, etc).
  - Asthma.
  - Food allergy.
  - Hay fever.
- Other medical and surgical history including concurrent diagnoses within the previous 12 months. For each condition, surgical procedure, or diagnosis, the start and stop dates will be recorded. It will also be recorded if the condition or diagnosis is ongoing.

Relevant medical history also includes diseases which are specifically listed as exclusion criteria and diseases for which treatments are listed as exclusion criteria or prohibited medications.

#### 11.2.4 Other assessments

The following tests will be conducted according to the schedule of trial procedures (Section 4):

- Hepatitis B virus testing (for more detail, see [Panel 10](#)).
- Hepatitis C virus antibody.
- HIV antibodies.
- Tuberculosis (*Mycobacterium tuberculosis* IFN- $\gamma$  release assay [or a PPD test if a requirement from the local health authorities]).
- SARS-CoV-2 (PCR).

### 11.3 Efficacy assessments

#### 11.3.1 Eczema Area and Severity Index (EASI)

EASI will be assessed by the investigator according to the schedule of trial procedures (Section 4). At an unscheduled visit, it will be at the discretion of the investigator if EASI should be assessed.

EASI is a validated measure used in clinical practice and clinical trials to assess the severity and extent of AD ([47](#)). The assessment will be based on the condition of the disease at the time of evaluation and not in relation to the condition at a previous visit. To reduce inter-assessor variability, the same investigator should, whenever possible, conduct all EASI assessments for a given subject during the entire trial.

THIS DOCUMENT CONTAINS CONFIDENTIAL INFORMATION AND MUST NOT BE COPIED OR MADE AVAILABLE TO ANY THIRD PARTY WITHOUT THE PRIOR WRITTEN CONSENT OF THE LEO PHARMA GROUP

EASI is a composite score ranging from 0 to 72 with higher scores indicating a more severe or more extensive condition. The score will be calculated as described in [Panel 7](#). Briefly, the investigator will assess the severity of 4 AD disease characteristics (erythema, induration/papulation, excoriation, and lichenification) on the 4 body regions (head/neck, trunk, upper extremities, and lower extremities). Severity will be assessed using the severity score scale presented in [Panel 8](#). For each body region, a severity sum score will be calculated and multiplied by an area score ([Panel 8](#)) and a weighting factor. The EASI score equals the sum of scores obtained for each body region ([Panel 7](#)).

### Reporting in eCRF

The body region, severity of the disease characteristics (erythema, induration/papulation, excoriation, and lichenification), and the area score will be recorded in the eCRF. Refer to [Appendix 3D](#) for principles for data entry in the eCRF.

### Panel 7: Calculation of the Eczema Area and Severity Index

Body region	Erythema	Induration/ papulation	Excoriation	Lichenification	Area score	Weighting factor	Score
Head/neck	(SS +	SS +	SS +	SS)	× AS	× 0.1	
Trunk	(SS +	SS +	SS +	SS)	× AS	× 0.3	
Upper extremities	(SS +	SS +	SS +	SS)	× AS	× 0.2	
Lower extremities	(SS +	SS +	SS +	SS)	× AS	× 0.4	
The EASI score is the sum of scores of the 4 body regions							(Range 0-72)

**Abbreviations:** AS = area score; EASI = Eczema Area and Severity Index; SS = severity score.

Modified from [\(48\)](#).

### Panel 8: Eczema Area and Severity Index severity score scale and area score scale

Severity score scale a	
0	None/absent
1	Mild
2	Moderate
3	Severe

a Half-scores (0.5, 1.5, 2.5) are allowed.

Area score scale	
0	0% affected area
1	1% to 9% affected area
2	10% to 29% affected area
3	30% to 49% affected area
4	50% to 69% affected area
5	70% to 89% affected area
6	90% to 100% affected area

THIS DOCUMENT CONTAINS CONFIDENTIAL INFORMATION AND MUST NOT BE COPIED OR MADE AVAILABLE TO ANY THIRD PARTY WITHOUT THE PRIOR WRITTEN CONSENT OF THE LEO PHARMA GROUP

### 11.3.2 Validated Investigator Global Assessment Scale for Atopic Dermatitis (vIGA-AD)

vIGA-AD will be assessed by the investigator according to the schedule of trial procedures (Section 4). At an unscheduled visit, it will be at the discretion of the investigator if the vIGA-AD should be assessed.

The vIGA-AD is an instrument used in clinical trials to assess the subject's global disease severity and is based on a 5-point scale ranging from 0 (clear) to 4 (severe) (Panel 9) (49). The assessment will be based on the condition of the disease at the time of evaluation and not in relation to the condition at a previous visit.

#### Reporting in eCRF

The disease severity assessment score will be recorded in the eCRF. Refer to [Appendix 3D](#) for principles for data entry in the eCRF.

#### Panel 9: Validated Investigator Global Assessment Scale for Atopic Dermatitis

Score	Morphological description
0 - Clear	No inflammatory signs of atopic dermatitis (no erythema, no induration/papulation, no lichenification, no oozing/crusting). Post-inflammatory hyperpigmentation and/or hypopigmentation may be present.
1 - Almost clear	Barely perceptible erythema, and barely perceptible induration/papulation, and/or minimal lichenification. No oozing or crusting.
2 - Mild	Slight but definite erythema (pink), slight but definite induration/papulation, and/or slight but definite lichenification. No oozing or crusting.
3 - Moderate	Clearly perceptible erythema (dull red), clearly perceptible induration/papulation, and/or clearly perceptible lichenification. Oozing and crusting may be present.
4 - Severe	Marked erythema (deep or bright red), marked induration/papulation, and/or marked lichenification. Disease is widespread in extent. Oozing or crusting may be present.

### 11.3.3 Body surface area involvement

The total BSA score will be assessed according to the schedule of procedures (Section 4).

The investigator will assess the total AD involvement for the whole body, i.e., head/neck, upper extremities, trunk, genitalia, and lower extremities, as a percentage of the total BSA. As a guidance for this estimate, the surface of a full, flat palm (including the 5 fingers) of an adult subject corresponds to approximately 1% of the total BSA.

THIS DOCUMENT CONTAINS CONFIDENTIAL INFORMATION AND MUST NOT BE COPIED OR MADE AVAILABLE TO ANY THIRD PARTY WITHOUT THE PRIOR WRITTEN CONSENT OF THE LEO PHARMA GROUP

## 11.3.4 Patient-reported outcomes

### 11.3.4.1 Overview

During the trial each subject should make individual assessments relating to their perception of their disease and quality of life. These should be performed independently of the investigator and prior to the investigator performing his/her efficacy assessments. At the screening visit (at the earliest Week -4), the subject's eligibility to participate in the trial needs to be established before the PROs can be completed.

The subject will be asked to complete the following PROs according to the schedule of trial procedures (Section 4).

- Worst Daily Pruritus NRS.
- POEM.
- DLQI.

Worst Daily Pruritus NRS will be completed daily in an eDiary. At Week -1 subjects will receive an eDiary device and eDiary training in using the device. At each visit between Week -1 and Week 32, the investigator or site staff will review the eDiary on the eDiary vendor portal and check compliance with eDiary completion.

In case of significant non-compliance, the investigator should remind the subject of the importance of adhering to the eDiary completion schedule. Subjects will be asked to return the eDiary at Week 32 or at their last visit in the trial.

POEM and DLQI will be completed in an electronic device by the subjects at the trial sites at the visits specified in the schedule of trial procedures (Section 4). At an unscheduled visit, it will be at the discretion of the investigator if POEM and/or DLQI should be assessed.

### 11.3.4.2 Worst Daily Pruritus NRS

Subjects will assess their worst itch severity over the past 24 hours using an 11-point NRS ('Worst Daily Pruritus NRS') with 0 indicating 'no itch' and 10 indicating 'worst itch imaginable'. Subjects will complete the Worst Daily Pruritus NRS as part of an eDiary each day from Week -1 until Week 32.

### 11.3.4.3 Patient-Oriented Eczema Measure (POEM)

The POEM is a validated questionnaire used to assess disease symptoms in AD patients in both clinical practice and clinical trials (50). The tool consists of 7 items each addressing a

THIS DOCUMENT CONTAINS CONFIDENTIAL INFORMATION AND MUST NOT BE COPIED OR MADE AVAILABLE TO ANY THIRD PARTY WITHOUT THE PRIOR WRITTEN CONSENT OF THE LEO PHARMA GROUP

specific symptom (itching, sleep, bleeding, weeping, cracking, flaking, and dryness). Subjects will score how often they have experienced each symptom over the previous week on a 5-point categorical response scale (0 = 'no days'; 1 = '1 to 2 days'; 2 = '3 to 4 days'; 3 = '5 to 6 days'; 4 = 'every day'). The total score is the sum of the 7 items (range 0 to 28) and reflects disease-related morbidity; a high score is indicative of a worse disease severity.

#### **11.3.4.4 Dermatology Life Quality Index (DLQI)**

The DLQI is a validated questionnaire with content specific to those with dermatology conditions (51). It consists of 10 items addressing the subject's perception of the impact of their skin disease on different aspects of their quality of life over the last week such as dermatology-related symptoms and feelings, daily activities, leisure, work or school, personal relationships, and the treatment. Each item is scored on a 4-point Likert scale (0 = 'not at all /not relevant'; 1 = 'a little'; 2 = 'a lot'; 3 = 'very much'). The total score is the sum of the 10 items (0 to 30); a high score is indicative of a poor quality of life.

### **11.4 Safety assessments**

#### **11.4.1 Vital signs**

Vital signs (blood pressure, pulse, and body temperature) will be assessed according to the schedule of trial procedures (Section 4). At an unscheduled visit, it will be at the discretion of the investigator if vital signs should be assessed.

For the first 3 IMP treatment visits (i.e., Visits 3, 4, and 5) subjects will be monitored after IMP administration for immediate drug reactions for a minimum of 1 hour with vital signs taken immediately after IMP administration as well as after 30 minutes ( $\pm$  5 minutes) and after 1 hour ( $\pm$  5 minutes), or until stable, whichever is later.

Vital signs (blood pressure, pulse, and body temperature) will be assessed following at least 5 minutes of rest. If a subject presents with an abnormal vital sign, the measurement of the vital sign can be repeated approximately 2–5 minutes later to verify the first measurement. Should the repeated measurement result in a normal value, the measurement must be repeated once more. If the third measurement verifies the second (normal) value, the first measurement should be considered false and the third measurement should be recorded in the eCRF. If the third measurement confirms the first measurement (abnormal), the second measurement should be considered false and the third measurement should be recorded in the eCRF. Only the last measurement considered true should be recorded in the eCRF.

THIS DOCUMENT CONTAINS CONFIDENTIAL INFORMATION AND MUST NOT BE COPIED OR MADE AVAILABLE TO ANY THIRD PARTY WITHOUT THE PRIOR WRITTEN CONSENT OF THE LEO PHARMA GROUP

In case of a clinically significant abnormal vital sign at screening and/or baseline, it will be at the discretion of the investigator if the subject should be included in the trial in accordance with exclusion criterion no. 27. During the trial, if a subject presents with a clinically significant abnormal vital sign, the investigator must take appropriate action, at their discretion.

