## After IMP administration

For the first 3 IMP treatment visits (i.e., Visits 3, 4, and 5), subjects will be monitored after IMP administration for immediate drug reactions for a minimum of 1 hour with vital signs taken immediately after IMP administration as well as after 30 minutes ( $\pm$  5 minutes) and after 1 hour ( $\pm$  5 minutes), or until stable, whichever is later. Vital signs will be documented in the eCRF.

As with any antibody, allergic reactions to dose administration are possible. The World Allergy Organisation has categorised anaphylaxis into 2 subgroups: allergic anaphylaxis (mediated by an immunologic mechanism) and nonallergic anaphylaxis (which has a nonimmunologic cause) (44). The clinical criteria for defining anaphylaxis for this trial are listed in [Appendix 5](#) and (45). Appropriate drugs, such as epinephrine, antihistamines, corticosteroids, etc., and medical equipment to treat acute anaphylactic reactions must be immediately available at trial sites, and trial personnel should be trained to recognise and respond to anaphylaxis according to local guidelines.

If an anaphylactic reaction occurs, a blood sample will be drawn from the subject as soon as possible after the event, at 60 minutes  $\pm$  30 minutes after the event, and at discharge for analysis of serum tryptase at the central laboratory.

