### Clinical criteria for diagnosing anaphylaxis

Anaphylaxis is highly likely when any one of the following 3 criteria are fulfilled:

- 1) Acute onset of an illness (minutes to several hours) with involvement of the skin, mucosal tissue, or both (e.g., generalised hives, pruritus or flushing, swollen lips-tongue-uvula)

AND AT LEAST ONE OF THE FOLLOWING:

- Respiratory compromise (e.g., dyspnoea, wheeze-bronchospasm, stridor, reduced peak expiratory flow [PEF], hypoxemia).
- Reduced blood pressure (BP) or associated symptoms of end-organ dysfunction (e.g., hypotonia [collapse], syncope, incontinence).

- 2) Two or more of the following that occur rapidly after exposure to a likely allergen for that patient (minutes to several hours):
  - Involvement of the skin-mucosal tissue (e.g., generalised hives, itch-flush, swollen lips-tongue-uvula).
  - Respiratory compromise (e.g., dyspnoea, wheeze-bronchospasm, stridor, reduced PEF, hypoxemia).
  - Reduced BP or associated symptoms (e.g., hypotonia [collapse], syncope, incontinence).
  - Persistent gastrointestinal symptoms (e.g., crampy abdominal pain, vomiting).

THIS DOCUMENT CONTAINS CONFIDENTIAL INFORMATION AND MUST NOT BE COPIED OR MADE AVAILABLE TO ANY THIRD PARTY WITHOUT THE PRIOR WRITTEN CONSENT OF THE LEO PHARMA GROUP

3) Reduced BP after exposure to known allergen for that patient (minutes to several hours):

- Infants and children: low systolic BP (age specific) or greater than 30% decrease in systolic BP.
- Adults: systolic BP of less than 90 mm Hg or greater than 30% decrease from that person's baseline.

THIS DOCUMENT CONTAINS CONFIDENTIAL INFORMATION AND MUST NOT BE COPIED OR MADE AVAILABLE TO ANY THIRD PARTY WITHOUT THE PRIOR WRITTEN CONSENT OF THE LEO PHARMA GROUP

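### The vital-sign repeat rule in Section 11.4.1 also covers the post-injection readings at Visits 3–5, so a brief abnormal reading can be replaced by a normal one in the vital-signs data

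*Combined protocol and SAP*

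**What the plan says.** Section 9.2 (After IMP administration) and Section 11.4.1 set the same monitoring for the first three treatment visits: "subjects will be monitored after IMP administration for immediate drug reactions for a minimum of 1 hour with vital signs taken immediately after IMP administration", then at 30 minutes (±5) and at 1 hour (±5), continuing for longer if the subject is not stable.

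Section 11.4.1 then gives the repeat rule. After an abnormal value, "the measurement of the vital sign can be repeated approximately 2–5 minutes later to verify the first measurement". This wording makes the first repeat optional. When it comes back normal, one more reading is compulsory, with no interval given. A second normal result then decides the matter: "If the third measurement verifies the second (normal) value, the first measurement should be considered false". The value entered is that last, normal one. In the opposite case, where the final reading is abnormal again, the normal second reading is the one discarded. The paragraph ends: "Only the last measurement considered true should be recorded in the eCRF".

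Nothing in Section 9.2 or 11.4.1 limits this rule to screening or pre-dose readings. Section 11.4.1 also says that vital signs "will be assessed following at least 5 minutes of rest".

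**The concern.** For a resting reading before dosing, an abnormal value followed by two normal ones is most simply explained as measurement error or chance fluctuation, and replacing it is reasonable. After an injection there is a further explanation: a real fall in blood pressure or rise in pulse that recovers within minutes. The rule treats quick normalisation as proof of error in both settings.

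What is at stake is the descriptive record of short-lived post-dose changes. Section 5.2 describes clinical experience with LEO 138559 as a single ongoing first-in-human trial, and Section 9.2 says that allergic reactions to dosing are possible. Appendix 5 uses a fall in blood pressure in its anaphylaxis criteria; the third of these reads in part "Adults: systolic BP of less than 90 mm Hg or greater than 30% decrease from that person's baseline". If the first value is not in the eCRF, nobody working from the trial database can see that it occurred.

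**Working it through.** No power, alpha or effect size enters this point, and the protocol gives no figure to reproduce. The check is a reading of the rule, interval arithmetic and a search for another route by which the value survives.

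**Which sequences lose an abnormal value.** Write A for abnormal and N for normal. Section 11.4.1 gives:

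- N: no repeat is called for; N is recorded.
- A, not repeated: A is recorded.
- A, A: the abnormality is confirmed; A is recorded.
- A, N, A: the second reading is classed as false; A is recorded.
- A, N, N: the first reading is classed as false; N is recorded.

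Only the last sequence removes an abnormal first reading. A measurement error produces that sequence, but so does a real change that has resolved by the second reading. The rule cannot separate the two.

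**Timing.** The second reading comes about 2–5 minutes after the first. No interval is stated before the third, so its time is the first gap plus an assumed second gap:

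- same gap assumed: 2 + 2 = 4 to 5 + 5 = 10 minutes;
- 1 minute assumed: 2 + 1 = 3 to 5 + 1 = 6 minutes;
- 5–10 minutes assumed: 2 + 5 = 7 to 5 + 10 = 15 minutes.

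Counting from the immediate post-dose reading, the next scheduled set is due no earlier than 30 − 5 = 25 minutes. That is 25 − 10 = 15 minutes after the latest third reading under the same-gap assumption, and 25 − 15 = 10 minutes under the longest gap tried. A change that had already resolved would not be expected to show at the next scheduled set.

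**Number of readings covered.** Three visits × 3 scheduled time points = 9 sets per subject. With 26 subjects per arm (Section 7.2), 9 × 26 = 234 in the active arm, and 9 × 52 = 468 in the trial. These are sets to which the rule could apply, not sets expected to be altered.

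**Recovery in the analysis.** Section 14.3.14.2 summarises the change in vital signs from baseline to each relevant visit. It describes no listing of abnormal vital signs and no summary by post-dose time point. Clinically significant physical findings (14.3.14.2), clinically significant ECGs (14.3.14.3) and out-of-range laboratory values (14.3.14.4) are all to be listed, and Section 11.4.4 keeps the individual ECG measurements as well as their average. Section 14.3.1 leaves the SAP to be finalised before unblinding, so a listing could be added there, but it could show only what the eCRF holds.

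**Recovery through adverse events.** The eCRF paragraph of Section 11.4.1 sends clinically significant abnormal vital signs at screening and baseline to medical history, and calls for AE reporting at subsequent visits. Visit 3 is both the baseline visit and the first dose. The matching ECG paragraph limits the medical-history rule to findings before the first dose; the vital-signs paragraph does not. For first-dose readings, AE capture therefore rests on Sections 13.2 and 13.3 and Appendix 1.

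**The case against.** The strongest reply is that one number is missing from one form while the event itself has its own route. AEs are collected at every visit, investigators must record changes they observe even if the subject reports none (Section 13.2), and Appendix 1 counts any unfavourable sign as an AE. This stands for clinically significant or symptomatic reactions. It is weaker for a brief, isolated change, because a reading that the protocol classes as false is less likely to be judged a clinically significant sign.

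A reader might infer more than the documents support:

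- *That transient drug reactions are deleted from the trial data.* What can be lost is a vital-sign value in the eCRF. AE reporting continues, and Appendix 3D requires source documents to be kept.
- *That these readings are the only scheduled means of detecting immediate reactions.* They are part of at least an hour of monitoring, with AE collection at the same visits. Tryptase is drawn after an anaphylactic reaction (Section 9.2) and may be tested for other injection reactions (Panel 10).
- *That the rule only ever favours normal values.* Only an abnormal first reading triggers it, but once triggered it is two out of three in either direction.
- *That the comparison with placebo is biased toward no difference.* The planned summaries are descriptive. The contrast would shrink only if brief changes were more frequent on active drug, and nothing in the documents shows that.
- *That an anaphylaxis classification would be lost.* In Appendix 5 the first two criteria need more than a fall in blood pressure, and the third requires a known allergen for that patient. A missing value could weaken the supporting record but would rarely decide the classification.
- *That the rest requirement contradicts the immediate post-dose reading.* Section 9.2 allows up to 10 minutes for the injections, so 5 minutes of rest could fall within them. The text is unclear rather than contradictory.

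**Conclusion.** The point holds in a limited form. Followed exactly, Section 11.4.1 replaces an abnormal post-dose reading with a normal one whenever the optional repeat is taken and both later readings are normal. Neither the next scheduled reading nor the planned by-visit summaries would be expected to bring the value back. The exposure is confined to brief, isolated changes that are not reported as AEs.

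The size is bounded but not estimated: no more than the 234 scheduled active-arm sets counted above, with no information on how often a reading would be abnormal, repeated and then normal twice. The 4–10 minute window is an assumption, since the protocol times only the first repeat. The conclusion depends on neither figure; it rests on the absence of any exception for post-dose readings. It concerns the completeness of the safety data and does not touch the primary efficacy analysis.

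**What to change.** In Section 11.4.1, limit the replacement of a reading classed as false to screening and pre-dose readings. For post-dose readings at Visits 3–5, enter every value in the eCRF with its clock time and a flag for repeats, and do not overwrite the first value. In Section 14.3.14.2 or the SAP, add a listing or descriptive summary by arm of abnormal or worst post-dose values. These changes concern data recording only and leave the handling of subjects as it is.

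Separately, state how the 5-minute rest requirement and the immediate post-dose reading are to be reconciled.

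The cost is a few sentences, repeat-reading fields on the vital-signs form, and one listing or table. The drawback is slightly more data entry and some noisy single values in the output, which the repeat flag lets a reader weigh.
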